7.3 Patient characteristics and baseline variables

Baseline demographics and clinical characteristics will be summarized by frequencies and percentages for categorical variables, continuous variables will be summarized by mean and standard deviation as well as quartiles. Group comparisons will be performed using Student t-tests or Wilcoxon Rank-Sum tests, as appropriate, for continuous variables. Fisher's Exact test will be used for categorical data. The following baseline demographic and clinical characteristics will be presented:

- Demographics
 - Age
 - Gender
 - Race
 - Ethnicity
 - Language
 - Marital status
 - Retirement
 - Living situation
 - Education
 - ApoE-e4 carrier status (yes or no)
- Clinical
 - ADAS-Cog12
 - Memory Composite (Story Recall, FCSRT)
 - MMSE
 - NPI
 - ADCS-ADL MCI
 - CDR-SB
 - Modified Hachinski
 - Logical Memory II Subscale (Wechsler Memory Scale)
 - Trail-making Test

7.4 Analysis of Primary outcome

Individuals in the active arm with Impel device will demonstrate slower rate of decline on ADAS-Cog12 in comparison to the placebo arm. Mixed Model repeated measures analysis of variance (MMRM) will be used to assess the difference between treatment groups in change from baseline for performance on the ADAS-Cog12. Participants will be included in the model if they have both a baseline and at least one post-baseline ADAS-Cog12. Change from baseline at each post-baseline visit for the ADAS-Cog12 will be the dependent variable. We will use a heterogeneous autoregressive AR(1) covariance structure. If the heterogeneous AR(1) covariance structure results in a lack of convergence, the following covariance structures will be used in sequence: heterogeneous compound symmetry covariance, homogeneous autoregressive AR(1) covariance, homogeneous compound symmetry covariance. Fixed effects in the model will include the following terms: (i) baseline ADAS-Cog12 score, (ii) treatment, (iii) visit, (iv) treatment-by-visit interaction, and (v) APOE- ϵ 4 genotype (Y/N) (vi) gender (vii) baseline MMSE score (viii) baseline age. Visits (baseline, month 3, month 6, month 9 and month 12) will be treated as a categorical variable. The null hypothesis is that the treatment difference between active and placebo with Impel device for the ADAS-Cog12 at month 12 is equal to zero.

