## 8.0 EARLY TREATMENT/STUDY DISCONTINUATION

The investigators at each site will make every reasonable effort to maximize participant retention. However, if an investigator removes a participant from treatment or study, or if a participant declines further treatment or study participation, an Early Discontinuation Visit will be completed as soon as possible following discontinuation of the study drug and or at time of study discontinuation. The Early Discontinuation Visit will contain the same assessments as the Month 12 visit, to allow collection of the main outcome measures. Depending on when the last LP or MRI was conducted, certain procedures may not be required at the Early Discontinuation Visit. If an in-person visit is not possible, site personnel will complete as much of the Early Discontinuation Visit as possible by telephone. All early treatment discontinuation participants will be strongly encouraged to complete all remaining visits through Month 12 visit.

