volumes (hippocampus, entorhinal cortex) will be analyzed with a similar strategy except that only baseline and month 12 values will be used. Other CSF biomarkers will be treated similarly in exploratory analyses. To address Secondary Aims 3 and 4, the predictive ability of APOE- $\epsilon$ 4 allele carriage and CSF biomarkers will be evaluated using RE models. A model will be developed predicting longitudinal ADAS-Cog12 response. CSF A $\beta$ 42 levels and APOE- $\epsilon$ 4 allele carriage will be included as fixed main effects along with treatment, time, and treatment-by-time interaction. A fixed effect for the interaction of A $\beta$ 42 and APOE- $\epsilon$ 4 will also be included. Potential confounders evaluated as described above will also be included as main effects. RE models make use of all observed data, and the assumption is made that any missing data is missing at random. Responses will be modeled as multivariate normal. Time will be treated as continuous and coded as months from baseline visit, (i.e. months = (exam date minus baseline date)/30.5). The correlation structure for the model will be first order autoregressive. As sensitivity analyses, both GEE (generalized estimating equations) and ANCOVA modeling will be performed. As an additional secondary (sensitivity) analysis, the above RE analysis will be performed treating time as categorical; differences between the active group and placebo group at 12 months will be assessed via contrasts in the least squares means; this analysis does not assume linearity over time. Associated p-values, standard errors of the differences, and 95 percent confidence intervals for each model will be presented for all analyses.

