### 15.3 Randomization

We will use a semi-crossover design (Jarjoura 2003). Initially, eligible participants will be randomized on a 1:1 schedule to receive placebo or 20 IU bid of INI using the following randomization strategy: ApoE-e4 carrier status (yes or no), gender, MMSE score (high, low). Study site and age will be weighted in a covariate-adaptive randomization strategy to achieve optimal balance between treatment arms on important factors that may influence treatment outcome. After 12 months of double-blinded treatment with placebo or 20 IU bid of insulin, all participants will receive 20 IU INI bid in a 6-month, open-label extension.

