3.1 Overview

The study will consist of a multisite, randomized, double-blind trial comparing the effects of INI (20 IU bid for total daily dose of 40 IU) and placebo for 12 months, followed by a 6-month open-label period in which all participants will receive INI. Participants with aMCI or probable mild AD (n=240-300) will be enrolled. The primary outcome measure will consist of the ADAS-Cog12. Secondary measures will include a memory composite, an executive function test, CDR Sum of Boxes (CDR-SB), and the ADCS-ADL MCI. The ADAS-Cog12 will be administered at 3 month intervals to optimize imputation of missing data. Other cognitive and functional measures will be administered at 6 month intervals. MRI measures of entorhinal cortex and hippocampal atrophy will be obtained at screening and 12 months. CSF and plasma biomarkers, as well as PBMcs and APOE- ϵ 4 allele carriage will also be assessed.

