3.5 Treatment Allocation

The two interventions are as follows:

- Group 1: active, 20 IU Humulin RU-100 bid for a total daily dose of 40 IU
- Group 2: placebo, matching placebo (sterile diluent)

Initially, eligible participants will be randomized on a 1:1 schedule to receive placebo or 20 IU bid of INI using the following randomization strategy:

- MMSE range (<=25 vs. >25)
- Site
- ApoE-e4 carrier status (yes or no)
- Gender (weight: 2)
- Age (<=70 vs. >70)

will be weighted in a covariate-adaptive randomization strategy to achieve optimal balance between treatment arms on important factors that may influence treatment outcome. After 12 months of double-blinded treatment with placebo or 20 IU bid of insulin, all participants will receive 20 IU INI bid in a 6-month, open-label extension.

4 Study Outcome Variables

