7.5 Analysis of Secondary Outcomes

Secondary Aims I

Individuals in the active arm with Impel device will demonstrate slower rate of decline on secondary outcomes including CDR-SB, memory composite (Story Recall and FCSRT), and ADCS-ADL MCI in comparison to the placebo arm. Mixed Model repeated measures (MMRM) models similar to the primary analysis will be used.

Secondary Aims V

To determine whether further improvement occurs after 18 months of treatment.

- The analysis will be the same as the primary analysis with data up to the month 18. The null hypothesis is that the treatment difference between active and placebo with Impel device for the ADAS-Cog12 at month 18 is equal to zero.
- Delayed-start analysis is to compare Δ_2 , the treatment differences between active and placebo at the month 18 (delayed-start period) with Δ_1 that at the end of the placebo-controlled period with noninferiority margin as 50% of Δ_1 [1, 2].

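### The primary ADAS-Cog12 model never allows an unstructured covariance or a robust standard error, so the Month 12 standard error can be too small; separately, site is left out

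*SAP*

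**What the plan says.** SAP 7.4 models change from baseline in ADAS-Cog12 at Months 3, 6, 9 and 12 with visit as a category, and tests the treatment difference at Month 12. On covariance it says: "We will use a heterogeneous autoregressive AR(1) covariance structure". If that does not converge, the order is "heterogeneous compound symmetry covariance, homogeneous autoregressive AR(1) covariance, homogeneous compound symmetry covariance". Neither an unstructured matrix nor a robust SE appears anywhere in the SAP.

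SAP 7.5 carries the model over to the open-label phase: "The analysis will be the same as the primary analysis with data up to the month 18". That makes six post-baseline visits. For the other outcomes SAP 3.1 says: "Other cognitive and functional measures will be administered at 6 month intervals", so they have only Months 6 and 12 in the blinded phase.

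On site, Protocol 15.3 says: "Study site and age will be weighted in a covariate-adaptive randomization strategy". SAP 3.5 lists MMSE range, site, APOE-ε4 status, gender and age as factors that "will be weighted in a covariate-adaptive randomization strategy to achieve optimal balance between treatment arms". The fixed effects in SAP 7.4 include baseline MMSE, APOE-ε4, gender and age, but not site.

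**The concern.** Heterogeneous AR(1) gives each visit its own variance but makes all correlations decay geometrically from a single parameter. At four visits it has 5 parameters, against 10 for unstructured. Neither document gives any visit correlations, so nothing shows that this shape fits. If participants decline at different rates, correlations stay high across long gaps and the spread of change grows with time. The single-parameter decay is then wrong, and a common variance is more wrong, because Month 12 has the largest spread.

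The covariance model sets the Month 12 SE and determines how dropouts' earlier scores inform the Month 12 mean. Under SAP 6.2, CDR-SB, the memory composite and ADCS-ADL-MCI can be declared significant only if this test succeeds. An SE that is too small therefore weakens the claimed 5% experiment-wise error rate at its first step.

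**Working it through.** **Inputs from the documents.** Four post-baseline visits; 240 to 300 participants, 1:1; two-sided alpha 0.05; SD of 12-month change 5.72; dropout 15 to 25%; differences of 1.6 to 2.6 points (Protocol 12.1). The documents give no SE or error rate for the planned model. As a check on the SD, the formula n = 2(SD × (1.960 + 0.842)/δ)² with δ = 2.2 gives 106.1. The printed entry of 239 at 25% dropout then equals 2 × 106.1 × 1.125 = 238.8, a total for both arms.

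**Assumed truths.** All have a 12-month change SD close to 5.7.

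- A: random intercept and slope, measurement SD 3, slope SD 3.86 per year
- B: the same form, 2 and 4.96
- C: the same form, 3.8 and 1.9
- D: heterogeneous AR(1) is true, correlation 0.75, SDs 4.3, 4.8, 5.3 and 5.7

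**Why the shape matters.** Before baseline adjustment, A to C imply Var(change at t) = slope² t² + 2 × error², and Cov(s, t) = slope² st + error².

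- *Correlation, truth A.* The adjacent correlations are 0.536, 0.609 and 0.685. AR(1) decay would make the Month 3 to Month 12 correlation their product, 0.22. The true value is (14.90 × 0.25 + 9)/(4.35 × 5.74) = 0.51.
- *Common variance, truth A.* The visit variances are 18.93, 21.72, 26.38 and 32.90, mean 24.98. The ratio to the Month 12 SD is √(24.98/32.90) = 0.87. The same sum gives 0.77 for B, 0.97 for C and 0.89 for D.

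**Month 12 model SE divided by true (sandwich) SE.** 200,000 simulated subjects, about 19% missing at Month 12, dropout depending on the last observed change.

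| Structure | A | B | C | D |
|---|---|---|---|---|
| Heterogeneous AR(1) (planned) | 0.978 | 0.942 | 1.001 | 1.000 |
| Heterogeneous CS | 0.985 | 0.974 | 0.997 | 1.008 |
| Homogeneous AR(1) | 0.872 | 0.773 | 0.975 | 0.876 |
| Homogeneous CS | 0.858 | 0.752 | 0.966 | 0.862 |

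Type I error is 2(1 − Φ(1.96 × ratio)). So 0.942 gives 6.5%, 0.974 gives 5.6%, and 0.752 gives 14%.

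**Simulated type I error.** 4,000 trials of n=240 per truth, REML, terms for visit, treatment by visit and baseline score. The Monte Carlo SE is √(0.05 × 0.95/4000), about 0.35 points.

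| Structure, model SE | A | B | D |
|---|---|---|---|
| Unstructured | 4.9% | 4.4% | 5.3% |
| Heterogeneous AR(1) | 5.3% | 6.0% | 5.3% |
| Heterogeneous CS | 5.3% | 5.1% | 4.8% |
| Homogeneous AR(1) | 8.4% | 12.3% | 8.5% |
| Homogeneous CS | 8.9% | 13.1% | 9.0% |

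With a sandwich SE every structure gave 4.5 to 5.6%. Unstructured was fitted in all 12,000 data sets and lost no precision when AR(1) was true (SE 0.789 for both).

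A separate large-sample calculation, with completely random dropout of 15 to 25% and slope SDs of 2 to 5.5, gave similar but wider ranges. Heterogeneous AR(1) was 0.918 to 1.000, heterogeneous CS 0.972 to 0.996, and the homogeneous structures 0.667 to 0.963.

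**Bias at Month 12.** Heterogeneous AR(1) minus unstructured on the same data, in points.

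- Same dropout rule in both arms, or AR(1) true: 0.00
- Score-dependent dropout in the active arm only: −0.13, −0.11 and −0.15 (A, B, C)
- In the placebo arm only: +0.13, +0.10 and +0.14
- Opposite dependence in the two arms: −0.26, −0.21 and −0.29

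**Month 18.** Six visits, about 25% missing: the heterogeneous AR(1) ratio is 0.937, 0.878, 0.990 and 1.000 for A to D. Type I error is at most 2(1 − Φ(1.96 × 0.878)) = 8.5%.

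**Site.** If arms are balanced within site and a share ICC of the variance lies between sites, omitting site widens the SE by a factor of 1/√(1 − ICC). For assumed ICCs of 0.01, 0.02, 0.05 and 0.10 that is 0.5%, 1.0%, 2.6% and 5.4%.

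**The case against.** The planned model itself does little harm. In simulation only truth B departs clearly from 5%, and B assumes that 4.96²/(4.96² + 2 × 2²) = 75% of the 12-month change variance is true difference in slope, which no figure in the documents supports. The equal-variance structures need two 5-parameter models to fail, although the 10-parameter one never failed in 12,000 data sets. A bias of 0.10 to 0.15 points is only 0.13 to 0.19 of an SE of 0.789 and needs dropout that differs by arm. Protocol 12.0 had already named a first-order autoregressive structure. It also plans multiple imputation and other checks: "As sensitivity analyses, both GEE (generalized estimating equations) and ANCOVA modeling will be performed". SAP 5.2 can be read as keeping those analyses. Protocol 8.0 limits missing data: "All early treatment discontinuation participants will be strongly encouraged to complete all remaining visits through Month 12 visit". Month 18 lies outside the gatekeeping sequence. Leaving out site is conservative. Unstructured may also fail in the small subgroups of SAP 7.8.

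Most of this stands as a limit on size, and the equal-variance figures should not drive the rating. It does not remove the point. The sensitivity analyses do not alter the p-value that gates the sequence, and prior specification of AR(1) is not evidence that it fits. The subgroup problem is met by keeping parsimonious heterogeneous fallbacks with a robust SE.

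**Conclusion.** The concern holds as a modest weakness in the gating test that should be corrected.

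- **Planned structure:** anything from no shortfall to a Month 12 SE about 6% too small, with type I error about 5.0 to 6.5%.
- **First fallback, heterogeneous CS:** close to nominal, about 4.8 to 5.6%.
- **Last two fallbacks:** materially too small, about 5.6 to 14%, but unlikely to be reached.
- **Bias:** none if the dropout rule is the same in both arms; up to 0.29 points, against planned differences of 1.6 to 2.6, only under opposite dropout patterns.
- **Site:** a separate, smaller loss of precision in the other direction.

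Every size rests on assumed covariances and dropout patterns, because the documents give only the 12-month SD. If AR(1) is true, the planned model has no shortfall. CDR-SB, the memory composite and ADCS-ADL-MCI to Month 12 are unaffected under the first-choice model, because with two visits heterogeneous AR(1) is already unstructured.

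**What to change.** Amend SAP 7.4 before unblinding:

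1. Make unstructured covariance with Kenward-Roger degrees of freedom the primary structure.
2. If it does not converge, use heterogeneous CS, then heterogeneous AR(1), each with a sandwich SE. The sandwich repairs the SE, not the dropout bias, so it is no substitute for unstructured as first choice.
3. Delete the two homogeneous structures.
4. Add site as a random intercept, or with small sites pooled. About 30 sites for 240 to 300 participants is 8 to 10 each.
5. Apply the covariance change to the Month 18 ADAS-Cog12 analysis in SAP 7.5.

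Adding diagnosis is optional: it is not an allocation factor, and baseline MMSE and ADAS-Cog12 capture part of it.

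The cost is one SAP paragraph, no new data and slightly more analysis work. Unstructured needs 10 covariance parameters instead of 5 at four visits, and 21 instead of 7 at six. The simulations did not include the random site term or the SAP's other covariates, so confirm convergence of the full model on blinded data before finalising the text.

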## **6.0 STUDY TIMELINE**

The approximate timeline for this four-year study is projected as follows: 1) approximately six months for study startup activities including FDA/IND submission, site IRB and regulatory approvals and the Investigator training meeting; 2) recruitment will last for approximately 18 months (for a total of 240-300 participants across about 30 sites); and 3) 18 months of follow up (last 6 months are open label)

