#### 12.0 STATISTICAL PLAN

The intent-to-treat (ITT) data set will include all eligible individuals who are randomized. The per-protocol (PP) data set will include all eligible participants who complete 12-month assessments for the primary analysis and receive 80% of prescribed treatment doses. To address the Primary Aim, the longitudinal scores for the first 12 months on the primary endpoint (ADAS-Cog12) as well as Secondary Aims (memory composite, Trails, CDR-SB, ADCS-ADL-MCI), will be analyzed using random effects (RE) models to assess the differences in the rate of change across treatment groups (insulin-treated vs. placebo). Fixed effects for time, treatment and time-by-treatment interaction will be included. The following covariates will be included in efficacy analyses if they meet the criteria described below: baseline MMSE, baseline age, years of education, gender, APOE- $\epsilon$ 4 carrier status, and diagnosis. Each covariate will be included in RE, ANCOVA, and GEE models only if the following two conditions are satisfied: 1) dissimilarity at baseline as measured by Fisher's exact test  $P < .1$ ; 2) a bivariate association exists between the covariate and the response (without regard to treatment) as measured by Spearman's correlation coefficient  $P < 0.15$ .

To address Secondary Aims 2 and 3, CSF biomarkers (A $\beta$ 42, tau, A $\beta$ 42/tau ratio) and MRI

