6.4 Covariates

Covariates to be included are specified for each analysis, when applicable.

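### Site is used to allocate participants but is left out of the primary MMRM, which makes the Month 12 test slightly conservative; a random site intercept fixes this at almost no cost

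*SAP*

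**What the plan says.** SAP 3.5 lists MMSE range, site, APOE-e4 carrier status, gender (weight 2) and age, and says that these "will be weighted in a covariate-adaptive randomization strategy to achieve optimal balance between treatment arms on important factors that may influence treatment outcome". Protocol 15.3 agrees that site is one of the factors: "Study site and age will be weighted in a covariate-adaptive randomization strategy". Protocol 6.0 plans "for a total of 240-300 participants across about 30 sites", which is 8 to 10 participants per site.

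The fixed effects in SAP 7.4 are baseline ADAS-Cog12, treatment, visit, treatment by visit, APOE-e4, and then "vi) gender (vii) baseline MMSE score (viii) baseline age". Within-participant correlation is handled by the covariance matrix alone: "We will use a heterogeneous autoregressive AR(1) covariance structure", with a sequence of simpler structures if that fails to converge. No random site effect is named.

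Nothing elsewhere restores site. SAP 6.4 says "Covariates to be included are specified for each analysis, when applicable", and the candidate covariates in Protocol 12.0 do not include site. SAP 7.5 analyses CDR-SB, the memory composite and ADCS-ADL MCI with models similar to the primary one. The documents give no reason for omitting site and plan no sensitivity analysis that includes it.

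**The concern.** Four of the five allocation factors are in the model and one is not. When allocation balances a factor that predicts outcome, the estimated treatment difference varies less from trial to trial, because the arms share that factor. A model that ignores the factor leaves its variance in the residual, so the reported standard error is larger than the true sampling variation of the estimate.

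Site could matter here. ADAS-Cog12 is administered by local psychometrists (Protocol 9.1.1 and 14.0) at about 30 sites, and the SAP itself describes the allocation factors as ones that may influence outcome. Under SAP 6.2 the primary p-value decides whether any of the three secondary clinical endpoints can be declared significant, so a small loss of precision on ADAS-Cog12 carries further than one endpoint.

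**Working it through.** **1. The plan's own figures.** Inputs from Protocol 12.1: SD 5.72, two-sided alpha 0.05, power 0.80. For a 2.1-point difference, n per arm = 2 × (1.960 + 0.842)² × 5.72² / 2.1² = 117 after rounding up. Both arms together are 234. Multiplied by (1 + 0.15/2) this gives 251.5, against 250 in Protocol Table 5. Read as a total over both arms with that inflation, all 55 cells agree within 1.1%. The calculation is a plain two-sample comparison with no site term.

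**2. Reported standard error.** With N = 240 and 15% dropout, 240 × 0.85 / 2 = 102 per arm. SE = 5.72 × √(2/102) = 0.801 points, a 95% half-width of 1.96 × 0.801 = 1.57 points.

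**3. Ceiling: perfect site balance.** Let ICC be the share of variance in 12-month change that lies between sites. The documents do not give it, so the values below are assumptions, including zero.
- True SE = 0.801 × √(1 − ICC), so the reported SE is too large by a factor 1/√(1 − ICC).
- Actual two-sided Type I error = 2 × [1 − Φ(1.96/√(1 − ICC))].
- Equivalent participants = 240 × ICC.

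**4. Realistic case: partial site balance.** With 30 small sites and four other factors competing, site is not perfectly balanced. Covariate-adaptive allocation on all five factors was simulated with 30 sites, n = 240, gender weight 2, an assumed biased-coin probability of 0.8 and 1,500 runs per non-zero ICC. A single-visit ANCOVA without site was compared with the same model plus a random site effect. For an SE excess x, equivalent participants = 240 × [1 − 1/(1 + x)²]; for example, x = 0.033 gives 240 × (1 − 0.937) = 15.

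| Assumed ICC | SE excess, partial balance | Participants of 240 | SE excess, perfect balance (ceiling) | Participants of 240 (ceiling) | Type I error (ceiling) |
|---|---|---|---|---|---|
| 0 | about 0% | 0 | 0% | 0 | 5.0% |
| 0.02 | 0.4% | 2 | 1.0% | 5 | 4.8% |
| 0.05 | 1.4% | 7 | 2.6% | 12 | 4.4% |
| 0.10 | 3.3% | 15 | 5.4% | 24 | 3.9% |

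A repeat with unequal sites and 15% dropout (600 runs per ICC) gave 0.8%, 1.6% and 3.3% at the three non-zero values, so differences of a few tenths of a percent are within simulation noise.

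**5. Direction.** In a further simulation at ICC 0.10 with no treatment effect (30 unequal sites, 2,000 runs), the mean reported SE without site was 0.799 against a true SD of the estimate of 0.770 at N = 240, and 0.716 against 0.676 at N = 300. The reported SE is too large, as the argument predicts.

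**6. What adding site costs.** With a random site effect and true ICC 0, the mean SE was 0.801 against 0.804 without site, so no precision is lost. With 29 unpooled fixed site terms at N = 240, the SE moved from 0.80 to 0.82 at ICC 0 and to 0.815 at ICC 0.02, stayed at 0.80 at ICC 0.05, and fell to 0.78 only at ICC 0.10. In 400 runs per ICC, the site variance was estimated as zero in 37% of runs at ICC 0.02 and 16% at ICC 0.05.

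**The case against.** The case for leaving the model alone has several parts.

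- **The ICC is assumed, and it may be low.** The outcome is change from baseline, adjusted for baseline score, MMSE, age, gender and APOE-e4. Stable differences between raters cancel in a change score, and ADAS-Cog raters must be trained and certified (Protocol 9.1.1). This stands: the omission is certain, its size is not, and at ICC 0 it has no effect.
- **A reader might infer that the primary test is invalid.** The documents do not support that. The omission widens the interval; it cannot create a false positive or bias the difference.
- **A reader might take the ceiling figures (5.4%, 24 participants) as the loss.** They need perfect balance within about 30 sites of 8 to 10 participants, on top of four other factors. The partial-balance column is the one to use.
- **A reader might infer that planned power is not met.** The sample size in Protocol 12.1 and SAP 3.4 never counted on a gain from site. What is lost is precision that the allocation makes available.
- **A reader might extend the point to the safety models in SAP 7.6.** Adverse events there are compared by Fisher's exact test, and routine laboratory samples go to a central laboratory (Protocol 10.4), so the rater argument does not carry over.
- **The calculations are for a single visit, not the full MMRM.** This stands. If site differences grow over the year, an intercept common to all visits will recover less than the table shows.
- **Small sites make site terms costly.** True of unpooled fixed effects, as step 6 shows, but not of a random intercept.

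**Conclusion.** The point holds as a small, conservative inefficiency. Site is an allocation factor in both documents and is absent from the primary model and from the similar models for the secondary clinical endpoints. If site explains some of the variance in 12-month change, the reported Month 12 standard error is too large by about 0.4% to 3.3% for ICC 0.02 to 0.10, and by nothing at ICC 0. At the top of that range the 95% half-width would fall from 1.57 to 1.57/1.033 = 1.52 points.

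The size rests on the assumed ICC, 30 sites, 240 participants and a biased coin of 0.8, none of which except the site count and total comes from the documents. The primary contrast is also restricted to the Impel device, and the number of participants in that comparison is not given, so the equivalents out of 240 are illustrative. The correction is worth making because it costs almost nothing and must be fixed in advance: a site term chosen after the results are seen would look post hoc.

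**What to change.** Before unblinding, amend SAP 7.4 and the clinical-outcome models in SAP 7.5 to add site as a random intercept, leaving the fixed effects and the heterogeneous AR(1) structure as they are. State three rules with it:

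1. If the site variance is estimated as zero, keep that fit. It equals the current model.
2. If the model does not converge after the covariance sequence already listed in SAP 7.4, drop the site term and use the model as now written.
3. Do not fall back to unpooled fixed site effects, which widen the standard error when site variance is near zero.

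The cost is a few lines of SAP text and one extra variance component.
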